1.1 PATHOPHYSIOLOGY

The current standard of care treatment for diabetic macular edema is anti VEGF therapy. Both 0.3mg Lucentis and Eylea have been shown to be superior to Avastin for treatment of diabetic macular edema in eyes with more advanced edema and poorer vision. 1.(DRCR Protocol T)

While there is a paucity of data of aqueous VEGF levels after Lucentis injection for DME, one study tested aqueous cytokines in response to bevacizumab injection in diabetic macular edema. Costagliola, et. al. demonstrated that aqueous VEGF levels remain lower but are still elevated compared to control patients in response to Avastin injections for DME(2). Based on Lucentis' tighter binding to VEGF (lower k_d) and greater penetration of the retina, we postulate that Lucentis injections will be much more effective at lowering aqueous VEGF levels explaining Lucentis' greater efficacy compared to Avastin in DRCR Protocol T. In the present protocol, we plan to use Lucentis 0.3 mg to demonstrate the VEGF levels will be lower compared to published results of aqueous VEGF levels after Avastin use. Furthermore we have preliminary data from a clinical trial at the Van Andel Institute demonstrating VEGF levels can predict response to anti-VEGF therapy. Clinical response will be measured by ETDRS visual acuity and spectral domain OCT central thickness. Finally, there is evidence that anti-VEGF therapy can normalize the pathologic intraocular environment beyond neutralizing VEGF. It is also well documented that anti VEGF therapy effects not only vascular endothelial growth factor but may also lower other inflammatory cytokines such as IL5, IL10 and interferon alpha. (3. Suzuki, et. al)

The present protocol will measure a number of cytokines in addition to VEGF in response to 0.3mg Lucentis therapy for diabetic macular edema. We have previously demonstrated a large number of cytokines can be measured in a small quantity of ocular fluid using aqueous or vitreous samples with a microbead assay. (4. J.White, L.Glazer, et.al). We propose that use of 0.3mg Lucentis, concurrently with aqueous taps for diabetic macular edema, will

document lower aqueous VEGF levels compared to other anti VEGF inhibitors (vs that in Costagliola, et. al [2]), will decrease the level of inflammatory cytokines, and will predict clinical response to Lucentis therapy demonstrated by visual acuity and OCT. Finally, showing efficacy with this dose of Lucentis should provide a good rationale for use of 0.3mg Lucentis in further DRCR studies.

1.2 TREATMENT OF SEVERE DIABETIC MACULAR EDEMA (DISEASE SPECIFIC)

The current best treatment options for these patients include Lucentis 0.3 or 0.5mg or Eylea. Present study will use the 0.3mg dose of Lucentis and perform an anterior chamber tap measuring aqueous cytokines before the first injection of Lucentis and just before the fourth intravitreal injection of 0.3mg Lucentis.

1.3 RANIBIZUMAB FOR SEVERE DIABETIC MACULAR EDEMA (DISEASE SPECIFIC)

Both Lucentis 0.3mg and 0.5mg dose and Eylea have been shown to be highly effective for severe diabetic macular edema with poor vision. The DRCR Protocol T did not test the 0.5mg dose of Lucentis against Eylea. We believe the 0.3mg dose will be especially effective in patients with recalcitrant diabetic macular edema (with probable markedly elevated VEGF levels.)

A positive result from the current study will give the DRCR and NEI further rationale to test the 0.3mg Lucentis dose in future protocols and also to compare the 0.3mg dose to Eylea.

1.4 NONCLINICAL EXPERIENCE WITH RANIBIZUMAB

1.4.1 Nonclinical Pharmacokinetics

The pharmacokinetics of ranibizumab have been investigated in rabbits and cynomolgus monkeys following intravitreal and intravenous administration. In both species, following intravitreal administration, ranibizumab was cleared from the vitreous humor with a half-life of 2–3 days. Following single intravitreal administration to cynomolgus monkeys, retinal concentrations of ranibizumab were approximately one-third of vitreous concentrations and declined in parallel with vitreous concentrations. In humans, the intravitreal

half-life of ranibizumab is estimated to be 7-8 days. Repeated intravitreal injections of ranibizumab can lead to detectable antibodies in serum in rabbits and cynomolgus monkeys.

1.4.2 Nonclinical Toxicology

A series of nonclinical studies of ranibizumab administered by intravitreal injection to cynomolgus monkeys have been performed (details regarding study design and results can be found in the Investigator Brochure).

1.4.3 Nonclinical Data Supporting the Anti-Edema Activity of Ranibizumab

In Studies 01-401E-1757 and 01-401G-1757, the effect of ranibizumab on vascular leakage was explored using a modified Miles assay in the guinea pig. Ranibizumab demonstrated a concentration-dependent effect of blunting the vascular permeability induced by VEGF. These results are consistent with the decrease in retinal vascular permeability as observed on optical coherence tomography (OCT) and fluorescein angiography in AMD and diabetic macular edema studies and further support the rationale for the use of ranibizumab in CRVO and BRVO, in which vascular permeability plays a significant role in the pathology

1.5 CLINICAL EXPERIENCE WITH RANIBIZUMAB

Ranibizumab has been or is being studied in more than 5000 subjects with diabetic macular edema and neovascular AMD in a number of Phase I, I/II, II, III, and IIIb clinical trials. Ranibizumab is contraindicated in patients with ocular or periocular infections and in those with known hypersensitivity to ranibizumab or any of the excipients in ranibizumab. Intravitreal injections, including those with ranibizumab, have been associated with endophthalmitis and retinal detachment. Proper aseptic injection technique should always be used when administering ranibizumab.

Increases in IOP have been noted within 60 minutes of intravitreal injection with ranibizumab. Therefore, IOP as well as perfusion of the optic nerve head should be monitored and managed appropriately. Serious adverse events related to the injection procedure have occurred in <0.1% of intravitreal injections include endophthalmitis, rhegmatogenous retinal detachment, and iatrogenic traumatic cataract. Other serious ocular adverse events observed among ranibizumab-treated

subjects and occurring in <2% of subjects included intraocular inflammation and increased IOP. The most common adverse reactions (reported \geq 6% higher in ranibizumab-treated subjects than control subjects) were conjunctival hemorrhage, eye pain, vitreous floaters, increased IOP, and intraocular inflammation.

Although there was a low rate (<4%) of arterial thromboembolic events (ATEs) observed in the ranibizumab clinical trials there is a potential risk of ATEs following intravitreal use of inhibitors of VEGF. The rate of ATEs in three studies (FVF2598g, FVF2587g, and FVF3192g) in the first year was 1.9% of subjects in the combined group of subjects treated with 0.3 mg or 0.5 mg ranibizumab compared with 1.1% of subjects in the control arms of the studies. In the second year of Study FVF2598g and FVF2587g, the rate of ATEs was 2.6% of subjects in the combined group of those treated with 0.3 mg or 0.5 mg ranibizumab compared with 2.9% of subjects in the control arm. The most common non-ocular adverse reactions observed in \geq 15% of ranibizumab-treated subjects that occurred more frequently than in control subjects included, nasopharyngitis, headache, and upper respiratory tract infection.

The Sailor study (FVF3689g) evaluated the safety of intravitreal ranibizumab in a large population of subjects with CNV secondary to AMD. Subjects in Cohort 1 (N=2378) were randomized (1:1) to receive ranibizumab at a dose level of 0.3 mg or 0.5 mg; subjects were masked to these dose levels. Treatment was administered monthly for three initial doses (Day 0, Month 1, and Month 2), with scheduled follow-up visits on Months 3,6,9, and 12. Retreatment after the first three injections was performed as needed, on the basis of predefined criteria with injections no more frequently than every 30 days.

Cohort 2 (N=1992) consisted of subjects enrolled after the majority of Cohort 1 subjects had been enrolled, with enrollment continuing until ranibizumab was approved or denied by the FDA for US marketing, and if approved, until commercially available or 30 September 2006, whichever was earlier. Subjects in Cohort 2 received open-label ranibizumab at the 0.5 mg dose level, with an initial injection on Day 0 followed by retreatment at the physician's discretion, no more frequently than every 30 days. Subjects were monitored for safety for a total of 12 months; safety information, including both serious and nonserious

adverse events, was collected at every clinic visit, with two formal safety visits scheduled at Months 6 and 12.

The study consisted of a 30-day screening period and a 1-year treatment period. Treatment duration was approximately 197 days for both dose groups in Cohort 1 and 144 days for subjects in Cohort 2. The mean follow-up time differed between Cohort 1 and Cohort 2, 337 days versus 254 days, respectively.

Ranibizumab was well tolerated, and the incidence of ocular SAEs and AEs was low and unrelated to dose. The rates of individual key ocular SAEs in Cohort 1 were < 1% and were similar across dose groups. Endophthalmitis or presumed endophthalmitis developed in 0.2% subjects in the 0.3-mg group and 0.4% subjects in the 0.5-mg group. The incidence of ocular inflammation, including iritis, uveitis, vitritis, and iridocylitis was 1.9% in the 0.3-mg group and 1.5% in the 0.5-mg group. Overall cataract rates were 5.4% (0.3 mg) and 6.0% (0.5 mg) and were similar when broken down by nuclear, subcapsular, and cortical subtypes. The rates of individual key ocular SAEs in Cohort 2 were <1%.

The rates of key non-ocular SAEs and AEs, including Antiplatelet Trialists' Collaboration (APTC) ATEs, MI, and vascular death were similar for cohorts 1 and 2 and 0.3- and 0.5-mg dose groups. The incidence of MI and non-ocular hemorrhage was similar across Cohort 1 dose groups. APTC ATEs, including vascular and unknown deaths, nonfatal MI, and nonfatal cardiovascular accidents, were similar across dose groups. During the 12-month study period, 0.7% of subjects in the 0.3-mg group and 1.2% of subjects in the 0.5-mg group suffered a stroke. The number of vascular deaths and deaths due to unknown cause did not differ across dose groups. Rates of key non-ocular SAEs in Cohort 2 were generally lower than those in Cohort 1.

Refer to the Ranibizumab Investigator Brochure or Lucentis® Package Insert for additional details regarding clinical safety experience with ranibizumab.

2. OBJECTIVES

2.1 Primary Objective

1. Measure aqueous VEGF levels in response to 0.3mg Lucentis dose for diabetic macular edema
2. Measure other cytokines response to 0.3 mg Lucentis dose for diabetic macular edema
3. Correlate clinical response (vision, spectral domain OCT retinal thickness level) to VEGF levels

2.2 Secondary Objectives

3. STUDY DESIGN

3.1 DESCRIPTION OF THE STUDY

Lucentis injections are the current standard of care for diabetic macular edema. The only deviation from the standard of care in the current protocol is an aqueous tap before the first Lucentis injection and the fourth Lucentis injection for diabetic macular edema. Such an approach has been shown to be extremely low risk for the patient. In a study from Pfahler et. al, (5), with 578 vitreous taps there were minimal complications. Vitreous taps are considered riskier than aqueous taps.

3.2 RATIONALE FOR STUDY DESIGN

Measuring aqueous anti VEGF levels may predict response to anti VEGF therapy. While there is not much data in DME, Compachario et al, (6), found that aqueous VEGF levels are higher in DME compared to retinal vein occlusions. A higher molar dose of Lucentis should theoretically be more effective in patients with recalcitrant macular edema and higher VEGF levels.

3.3 OUTCOME MEASURES

3.3.1 Primary Outcome Measures

1. VEGF levels before and after Lucentis injections
2. In addition to measuring VEGF, Multiplex bead-based immunoassay will be used for simultaneous measurement of 39 cytokines and chemokines in the aqueous samples, before and after Lucentis injections. (See White and Glazer. 4)

3.3.2 Secondary Outcome Measures

1. ETDRS vision before and after Lucentis injection
2. Spectral domain OCT retinal thickness before and after Lucentis injection

3.3 SAFETY PLAN

A current IRB exists with [name] lab at MSU to analyze vitreous specimens. See attached. The study is funded by Genentech, and an IRB will be obtained for the current protocol and material transfer agreement will be consummated with [name] to send the aqueous samples directly to her lab.

Safety concerns, the only deviation from current standard of care in the current protocol is an aqueous tap before the first Lucentis injection and before the fourth Lucentis injection. We have previously conducted a clinical trial similar to this with the Van Andel Institute for macular degeneration without any complications. Furthermore, Pfahler (5) performed more than 578 vitreous taps without significant morbidity, which are considered riskier than aqueous taps. Compachairo et al (7) performed aqueous taps on 59 patients receiving Lucentis without morbidity. This is six times the number of patients proposed in this clinical trial.

3.5 compliance with Laws and Regulations

This study will be conducted in accordance with current U.S. Food and Drug Administration (FDA) Good Clinical Practices (GCPs), and local ethical and legal requirements.

4. MATERIALS AND METHODS

4.1 SUBJECTS

4.1.1 Subject Selection

Ten patients will be selected with diabetic macular edema using entry criteria from DRCR protocol T.

4.1.2 Inclusion Criteria

Age \geq 18 years

- Diagnosis of diabetes mellitus (type 1 or type 2)
- Able and willing to provide informed consent
- Best corrected E-ETDRS visual acuity score ≤ 78 (ie 20/32 or worse) and ≥ 24 (ie 20/320 or better)
- On clinical exam, definite retinal thickening due to diabetic macular edema involving the center of the macula
- DME present on OCT (central subfield thickness on OCT ≥ 250 microns)
- Media clarity, pupillary dilation, and individual cooperation sufficient for adequate fundus photographs

- DME with DR score DRSS 47-53

4.1.3 Exclusion Criteria

Significant renal disease, defined as a history of chronic renal failure requiring dialysis or kidney transplant

- A condition that, in the opinion of the investigator, would preclude participation in the study (e.g. unstable medical status including blood pressure, cardiovascular disease, and glycemic control)
- Individuals in poor glycemic control who, within the last four months, initiated intensive insulin treatment (a pump or multiple daily injections) or plan to do so in the next four months should not be enrolled
- Participation in an investigational trial within 30 days of randomization that involved treatment with any drug that has not received regulatory approval for the indication being studied at time of study entry
- Known allergy to any component of the study drug
- Blood pressure >180/100 (systolic above 180 OR diastolic above 110)
- Myocardial infarction, other acute cardiac event requiring hospitalization, stroke, transient ischemic attack, or treatment for acute congestive heart failure within 4 months prior to randomization
- Systemic anti-VEGF or pro-VEGF treatment within 4 months prior to randomization or anticipated use during the study
- For women of childbearing potential: pregnant or lactating or intending to become pregnant within the next 24 months
- Individual is expecting to move out of the area of the clinical center to an area not covered by another clinical center during the first 12 months of the study
- Macular edema is considered to be due to a cause other than diabetic macular edema
- An ocular condition is present such that, in the opinion of the investigator, visual acuity loss would not improve from resolution of

macular edema (eg foveal atrophy, pigment abnormalities, dense subfoveal hard exudates, nonretinal condition)

- An ocular condition is present (other than diabetes) that, in the opinion of the investigator, might affect macular edema or alter visual acuity during the course of the study (e.g. vein occlusion, uveitis or other ocular inflammatory disease, neovascular glaucoma, etc.)
- Substantial cataract that, in the opinion of the investigator, is likely to be decreasing visual acuity by three lines or more
- History of an anti-VEGF treatment for DME in the past 12 months or history of any other treatment for DME at any time in the past four months (such as focal grid macular photocoagulation, intravitreal or peribulbar corticosteroids)
- History of pan-retinal photocoagulation within four months prior to randomization or anticipated need for pan-retinal photocoagulation in the six months following randomization
- History of anti-VEGF treatment for a disease other than DME in the past 12 months
- History of major ocular surgery (including vitrectomy, cataract extraction, scleral buckle, any intraocular surgery, etc.) within four months or anticipated within the next six months following randomization
- History of YAG capsulotomy performed within 2 months prior to randomization
- Aphakia
- Exam evidence of external ocular infection, including conjunctivitis, chalazion, or significant blepharitis

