5.5 VITAL SIGNS

Pulse and blood pressure will be measured at protocol-specified study visits (see Section 4.5).

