- Hospitalization or prolonged hospitalization required to allow efficacy measurement for the study or
- Hospitalization or prolonged hospitalization for scheduled therapy of the target disease of the study.

e. Pregnancy

If a female subject becomes pregnant while receiving investigational therapy or within 90 days after the last dose of study drug, a report should be completed and expeditiously submitted to the Genentech, Inc. Follow-up to obtain the outcome of the pregnancy should also occur. Abortion, whether accidental, therapeutic, or spontaneous, should always be classified as serious, and expeditiously reported as an SAE. Similarly, any congenital anomaly/birth defect in a child born to a female subject exposed to the 0.3mg Lucentis should be reported as an SAE.

f. Post-Study Adverse Events

The investigator should expeditiously report any SAE occurring after a subject has completed or discontinued study participation if attributed to prior 0.3mg Lucentis exposure. If the investigator should become aware of the development of cancer or a congenital anomaly in a subsequently conceived offspring of a female subject who participated in the study, this should be reported as an SAE.

g. Reconciliation

The Sponsor agrees to conduct reconciliation for the product. Genentech and the Sponsor will agree to the reconciliation periodicity and format, but agree at minimum to exchange quarterly line listings of cases received by the other party.

If discrepancies are identified, the Sponsor and Genentech will cooperate in resolving the discrepancies. The responsible individuals for each party shall handle the matter on a case-by-case basis until satisfactory resolution. The Sponsor shall receive reconciliation guidance documents within the 'Activation Package'.

h. AEs of Special Interest (AESIs)

AEs of Special Interest are defined as a potential safety problem, identified as a result of safety monitoring of the Product.

The Lucentis Events of Special Interest are:

- Retinal pigment epithelial tear
- Increased intraocular pressure to > 30mm Hg not responsive to maximal topical IOP-lowering drugs measured on 2 separate days
- Traumatic cataract
- Endophthalmitis
- Intraocular inflammation of greater than 2+ cells (including vitritis and uveitis)
- Retinal detachment
- ATEs, including stroke

i. Adverse Event Reporting

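### The blood-pressure exclusion in Section 4.1.3 prints two diastolic limits, 100 and 110, and nothing else in the document settles which applies

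*Combined protocol and SAP*

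**What the plan says.** The exclusion list in Section 4.1.3 contains one numeric blood-pressure rule: "Blood pressure >180/100 (systolic above 180 OR diastolic above 110". The systolic limit is 180 in both halves. The diastolic limit is 100 in the shorthand and 110 in the parenthesis.

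Blood pressure is named in two other places, neither with a number:

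- Another bullet of Section 4.1.3 lets the investigator exclude a patient for "unstable medical status including blood pressure, cardiovascular disease, and glycemic control".
- Section 5.5 says "Pulse and blood pressure will be measured at protocol-specified study visits (see Section 4.5".

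On where the criteria come from, Section 4.1.1 says "Ten patients will be selected with diabetic macular edema using entry criteria from DRCR protocol T". The document does not reproduce that protocol's blood-pressure limit.

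**The concern.** An eligibility threshold has to give one answer for each patient, and this one does not. A screener who acts on the shorthand turns away a patient with a diastolic pressure of 105; one who acts on the parenthesis enrols the same patient. A monitor could later call that enrolment valid or call it an eligibility deviation, and the protocol has no rule of precedence to settle the matter.

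The plan does not state what the limit is for. A cardiovascular safety purpose is a reasonable inference. Section 1.5 warns that "there is a potential risk of ATEs following intravitreal use of inhibitors of VEGF", and Section 5.6.2(h) lists "ATEs, including stroke" among the events of special interest. The bullet in Section 4.1.3 that follows the blood-pressure rule covers recent events of the same kind: "Myocardial infarction, other acute cardiac event requiring hospitalization, stroke, transient ischemic attack". If that is the purpose, the ambiguity bears on which patients are screened out for safety. It has little bearing on the biomarker results.

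**Working it through.** No sample size, power or error rate depends on this limit, so there is no planned figure to reproduce. The check compares the two halves of the bullet and then looks for anything in the document that decides between them.

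**Inputs (all from Section 4.1.3).** Systolic limit: 180 in both halves. Diastolic limit: 100 in the shorthand, 110 in the parenthesis. Operator: OR, printed only in the parenthesis.

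**Step 1: write out the two rules.** SBP is systolic and DBP is diastolic pressure, in mmHg.

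- Rule A (shorthand, borrowing the printed OR): exclude if SBP > 180 or DBP > 100.
- Rule B (parenthesis): exclude if SBP > 180 or DBP > 110.

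**Step 2: find where they differ.**

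| Region | Rule A | Rule B |
|---|---|---|
| SBP > 180, any DBP | exclude | exclude |
| SBP ≤ 180, DBP > 110 | exclude | exclude |
| SBP ≤ 180, DBP 101 to 110 | exclude | admit |
| SBP ≤ 180, DBP ≤ 100 | admit | admit |

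The rules conflict in the third row only. In whole mmHg the band holds 110 − 100 = 10 diastolic values. A reading of 170/105 falls inside it.

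**Step 3: try the other reading of the shorthand.** The shorthand has no operator of its own. Read as AND, it would exclude only if SBP > 180 and DBP > 100. It would then admit 190/95 (diastolic not above 100) and 170/115 (systolic not above 180), both of which Rule B excludes. So neither reading of the shorthand reproduces the parenthesis. OR is used for the band because it is the only operator the document prints.

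**Step 4: look for a tie-breaker.** Blood pressure is mentioned three times: twice in Section 4.1.3 and once in Section 5.5. Only one mention, the bullet itself, carries a number. The flowchart in Appendix A has no blood-pressure row. Section 4.1.1 names the source of the entry criteria without giving its limit. The document therefore does not show which number was intended.

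The number of patients who would fall in the band cannot be computed, because the document gives no blood-pressure distribution. It may be zero.

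**The case against.** The strongest reply is that this is an obvious slip of one digit. The parenthesis names both components, gives each a limit and states the operator, whereas the shorthand is not a complete rule. The 10-value band exists only because the OR has been carried over to the shorthand. A sensible reader would apply 110. This makes 110 the likelier intention, but the protocol does not say that the parenthesis governs, and staff could still act on "Blood pressure >180/100".

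Second, the plan has partial cover. The investigator can exclude a worrying patient at 170/105 under the discretionary bullet, and Section 4.1.1 tells staff which source to consult. Both points are fair. But discretion does not say which numeric limit applies, and the source's limit is not printed here.

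Third, the safety argument is inferred. The passages on arterial thromboembolic events (ATEs) do not mention blood pressure, and the ATE rates in Section 1.5 are mixed: 1.9% on ranibizumab against 1.1% on control in the first year, and 2.6% against 2.9% in the second. That is correct. Nothing in the document shows harm from admitting patients in the band, and the finding does not depend on such harm.

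Fourth, nothing in the analysis turns on this in a 10-patient pilot with no formal sample size calculation. That is also correct, and it limits the weight of the point. It does not make the rule consistent.

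**Conclusion.** The concern holds. One operative exclusion bullet gives two diastolic limits, and the document contains nothing that resolves them. The conflict covers systolic pressure not above 180 with diastolic pressure of 101 to 110 mmHg. That size rests on reading the shorthand with the OR printed in the parenthesis; the AND reading also disagrees with the parenthesis, in different regions.

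The point should be corrected but is not critical. It affects eligibility and safety screening of possibly no patients, and its effect on the VEGF and cytokine outcomes is minor. That 100 is the slip is probable but cannot be confirmed from the document, and the cardiovascular purpose of the limit is an inference.

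**What to change.** State one diastolic limit in Section 4.1.3. The provisional choice is to change the 100 in the shorthand to 110 and leave the parenthesis as it stands, because the parenthesis is the complete rule. Before enrolment, the medical lead should confirm the number against the source criteria named in Section 4.1.1. If the source gives 100, keep the shorthand and change the parenthesis to 100 instead.

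The cost is one number in one bullet, with no new visit, procedure or patient.
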